8.2 Populations for Analyses

- All Enrolled Subjects: All subjects who have signed an ICF and are registered into the IVRS.
- All Treated Subjects: All subjects who received at least one dose of study medication.
- The PK data set includes all available concentration-time data from the subjects who received any BMS-986156 [REDACTED].
- The Immunogenicity data set consists of all available immunogenicity data from the subjects who receive BMS-986156 or nivolumab and have a baseline and at least one post treatment immunogenicity measurement.

[REDACTED]

Analyses of safety, extent of exposure, [REDACTED] PK, efficacy and immunogenicity will be based on all treated subjects.

8.3 Endpoints

8.3.1 Primary Endpoint(s)

The primary objective of the study is to establish MTD/MAD/alternate dose(s). The assessment of safety will be based on the incidence of AEs, SAEs, AEs leading to discontinuation, and deaths. In addition clinical laboratory test abnormalities will be examined.

AEs and laboratory values will be graded according to the NCI CTCAE version 4.03.

8.3.2 Secondary Endpoint(s)

8.3.2.1 Pharmacokinetics

Pharmacokinetics of BMS-986156 will be characterized by estimation of PK parameters as defined in [Section 5.5](#).

8.3.2.2 Efficacy

The second antitumor activity of BMS-986156 alone and BMS-986156 in combination with nivolumab will be measured by ORR and duration of response based on RECIST 1.1. Disease assessment with CT and/or MRI as appropriate will be performed at baseline and every 8 weeks during Treatment Phase until disease progression per RECIST v1.1, or until confirmed disease progression for subjects treated beyond progression [defined as an additional 10% or greater increase in tumor burden volume from time of initial progression (including all target lesions and new measurable lesions)], discontinuation of treatment or withdrawal from study. Subjects having received local palliative therapy will be documented as having had disease progression for the purpose of efficacy analyses.

- Best overall response (BOR): defined as the best response designation over the study as a whole, recorded between the dates of first dose until the last tumor assessment prior to subsequent therapy. BOR is assessed by investigator (BIRC) per RECIST 1.1 criteria.
- ORR is defined as the proportion of all treated subjects whose BOR is either a CR or PR.
- Duration of response, computed for all treated subjects with a BOR of CR or PR, is defined as the time between the date of first response and the date of disease progression or death, whichever occurs first.
- PFSR at 24 *Weeks*: The proportion of treated subjects remaining progression free and surviving at 24 *weeks*. The proportion will be calculated by the K-M estimate which takes into account censored data.

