- Safety Outcome Measures:** Safety assessments will be based on comprehensive medical review of adverse event reports, vital sign measurements, ECGs, physical examinations, and results of laboratory tests. AEs will be coded using the most current version of Medical Dictionary for Regulatory Activities (MedDRA) and the incidence of observed adverse events will be tabulated and reviewed for potential significance and clinical importance. Adverse events will be assessed continuously during the study and for 100 days after the last treatment. Both AEs and laboratory tests will be graded using the NCI CTCAE v4.03.
- Efficacy Measures:** Disease assessment with computed tomography (CT) and/or magnetic resonance imaging (MRI), as appropriate, will be performed at baseline and every 8 weeks until disease progression. Once disease progression is noted, no more protocol required tumor assessments are needed unless treatment is continued beyond progression. For those subjects who continue study therapy beyond initial disease progression, tumor assessments will continue every 8 weeks until confirmed disease progression or study treatment is discontinued. Tumor responses will be derived as defined by RECIST v1.1 based on recorded tumor measurements (see [Appendix 3](#)).
- Pharmacokinetic Measures:** Serial serum samples will be collected from all subjects at specified time points to evaluate concentrations of BMS-986156. PK parameters such as C_{max}, C_{trough}, T_{max}, T-HALF, AUC (TAU), CLT, and accumulation index (AI) will be derived, if feasible, from serum concentration versus time data. [REDACTED]
- Immunogenicity Measures:** Serum samples to evaluate development of anti-drug antibody (ADA) response to BMS-986156 alone, and in combination with nivolumab will be collected at specified time points.

Statistical Considerations:

Sample Size:

Dose Escalation:

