3.11.1 Treatment Beyond Disease Progression

As described in [Section 1.1.3](#) accumulating evidence indicates a minority of subjects with solid tumors treated with immunotherapy may derive clinical benefit despite initial evidence of PD. Subjects will be permitted to continue on treatment beyond initial RECIST v1.1 (see [Appendix 3](#)) defined PD, as long as they meet the following criteria:

- Investigator-assessed clinical benefit, and do not have rapid disease progression
- Continue to meet all other study protocol eligibility criteria
- Tolerance of study drug
- Stable performance status
- Treatment beyond progression will not delay an imminent intervention to prevent serious complications of disease progression (eg, CNS metastases)
- Subject provides written informed consent prior to receiving any additional nivolumab or BMS-986156 treatment, using an ICF describing any reasonably foreseeable risks or discomforts, or other alternative treatment options
- Absence of signs or symptoms indicating disease progression

The assessment of clinical benefit should take into account whether the subject is clinically deteriorating and unlikely to receive further benefit from continued treatment. All decisions to continue treatment beyond initial progression must be discussed with the BMS Medical Monitor

and an assessment of the risk/benefit of continuing with study therapy must be documented in the study records. Subjects will be re-consented to explain the rationale for this ongoing treatment.

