3.11.1.1 Discontinuation Due to Further Progression (Confirmed Progression)

Subjects should discontinue study therapy upon further evidence of further progression, defined as an additional 10% or greater increase in tumor burden volume from time of initial progression (including all target lesions and new measurable lesions).

The tumor burden volume from time of initial progression should be used as the reference baseline for comparison with the post-progression assessment.

Any new lesion considered non-measurable at the time of initial progression may become measurable and therefore must be included in the tumor burden measurement as follows:

New lesions are considered measurable at the time of initial progression if the longest diameter is at least 10 mm (except for pathological lymph nodes, which must have a short axis of at least 15 mm).

For statistical analyses that include the investigator-assessed progression date, subjects who continue treatment beyond initial investigator-assessed, RECIST v1.1-defined progression will be considered to have investigator-assessed progressive disease at the time of the initial progression event.

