4 RESPONSE CRITERIA

4.1 Time point response

A response assessment should occur at each time point specified in the protocol.

For subjects who have **measurable disease** at baseline Table 4.1-1 provides a summary of the overall response status calculation at each time point.

Target lesions	Non-target lesions	New lesions	Overall response
CR	CR	No	CR
CR	Non-CR/non-PD	No	PR
CR	Not evaluated	No	PR
PR	Non-PD or not all evaluated	No	PR
SD	Non-PD or not all evaluated	No	SD
Not all evaluated	Non-PD	No	NE
PD	Any	Yes or No	PD
Any	PD	Yes or No	PD
Any	Any	Yes	PD

CR = complete response, PR = partial response, SD = stable disease, PD = progressive disease, NE =not evaluable.

Missing assessments and not evaluable designation

When no imaging/measurement is done at all at a particular time point, the subject is **not evaluable (NE)** at that time point. If only a subset of lesion measurements are made at an

assessment, the case is also considered NE at that time point, unless a convincing argument can be made that the contribution of the individual missing lesion(s) would not have changed the assigned time point response.

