4.2 Best overall response: All timepoints

The *best overall response* is determined once all the data for the subject is known. It is the best response recorded from the start of the study treatment until the date of objectively documented progression based on RECIST v1.1, taking into account any requirement for confirmation, or the date of subsequent anti-cancer therapy, whichever occurs first in the study. The subject’s best overall response assignment will depend on the findings of both target and non-target disease and will also take into consideration the appearance of new lesions.

Best response is defined as the best response across all time points with subsequent confirmation. Complete or partial responses may be claimed only if the criteria for each are met at a subsequent time point as specified in the protocol (generally 4 weeks later).

In this circumstance, the best overall response can be interpreted as specified in Table 4.2-1. When SD is believed to be best response, it must meet the protocol specified minimum time from baseline. Measurements must have met the SD criteria at least once after study entry at a minimum interval (in general not less than 6–8 weeks) that is defined in the study protocol.

Overall response	Overall response	BEST overall response
First time point	Subsequent time point	
CR	CR	CR
CR	PR	SD, PD or PR ^a
CR	SD	SD provided minimum criteria for SD duration met, otherwise, PD
CR	PD	SD provided minimum criteria for SD duration met, otherwise, PD
CR	NE	SD provided minimum criteria for SD duration met, otherwise NE
PR	CR	PR
PR	PR	PR

Table 4.2-1: Best overall response when confirmation of CR and PR IS required		
Overall response	Overall response	BEST overall response
First time point	Subsequent time point	
PR	SD	SD
PR	PD	SD provided minimum criteria for SD duration met, otherwise, PD
PR	NE	SD provided minimum criteria for SD duration met, otherwise NE
NE	NE	NE

CR = complete response, PR = partial response, SD = stable disease, PD = progressive disease, NE = not evaluable.

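### The statistical section lets best overall response run past progression while Appendix 3 stops it there, so a response that first appears after progression counts under one text and not the other.

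*Combined protocol and SAP*

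**What the plan says.** Two places in the combined protocol and SAP define BOR.

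- **Section 8.3.2.2** takes the best designation across the entire study, "recorded between the dates of first dose until the last tumor assessment prior to subsequent therapy". Progression does not close this window. ORR is the proportion of all treated subjects whose BOR is CR or PR. Duration of response (DOR) is computed only for those responders, as "the time between the date of first response and the date of disease progression or death, whichever occurs first".
- **Appendix 3, section 4.2** takes the best response from the start of treatment "until the date of objectively documented progression based on RECIST v1.1" or to the date of subsequent anti-cancer therapy, whichever is earlier, and takes account of confirmation.

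Section 3.11.1 provides for treatment after progression: "Subjects will be permitted to continue on treatment beyond initial RECIST v1.1"-defined PD if listed criteria are met. For these subjects the synopsis (Efficacy Measures) says that "tumor assessments will continue every 8 weeks until confirmed disease progression or study treatment is discontinued". Section 3.11.1.1 adds that, for analyses using the investigator-assessed progression date, they "will be considered to have investigator-assessed progressive disease at the time of the initial progression event".

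On the assessor, 8.3.2.2 states: "BOR is assessed by investigator (BIRC) per RECIST 1.1 criteria". Section 5.4 has the investigator assess and report response. Appendix 3, section 1, says only that central assessment is a possibility.

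**The concern.** BOR decides who is a responder, and so who enters both ORR and DOR. If its window is open after progression in one text and closed in the other, a subject whose first confirmed CR or PR follows initial PD is classified differently depending on which text the programmer follows.

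Under the 8.3.2.2 window the results also contradict each other. The same subject is a responder for ORR and a progression event for PFSR, and has a DOR that ends before it starts. Someone would have to invent a rule for that value, possibly after seeing the data.

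ORR is a secondary, descriptive endpoint. It is one input to the totality-of-data decisions in sections 3.7 and 8.1.2, so no formal threshold is at risk. What is at risk is a coherent, reproducible set of efficacy results.

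**Working it through.** **1. The plan's own ORR figures (section 8.1.2, n = 40).** The one-sided 90% Clopper-Pearson lower limit is the Beta quantile (0.10; x, n − x + 1).

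- x = 10 gives 16.15%; x = 15 gives 27.14%. The plan states 16% and 27%.
- With true ORR 40%: P(≥12) = 0.9291, P(≥13) = 0.8715, P(≤11) = 0.0709. The plan states 93%, 87% and 7%.

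These figures reproduce. They do not say which BOR window defines a response.

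**2. Can the two windows differ for a real subject?** Appendix 3, section 3.1, judges PR against the baseline sum. It judges PD against the smallest sum on study, and requires at least a 20% and a 5 mm increase. Take a hypothetical subject with no new lesion and no non-target progression:

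| Time | Target sum | Time point response |
|---|---|---|
| Baseline | 100 mm | – |
| Week 8 | 125 mm (+25%, +25 mm) | PD |
| Week 16 | 68 mm (−32% from baseline) | PR |
| Week 24 | 66 mm (−34% from baseline) | PR, confirmed at least 4 weeks later |

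No subsequent therapy is given, and treatment continues under 3.11.1.

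**3. Apply each text.**

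| Quantity | Section 8.3.2.2 with 3.11.1.1 | Appendix 3, section 4.2 |
|---|---|---|
| BOR window ends | last scan before subsequent therapy | week 8 (PD) |
| ORR | responder | non-responder |
| PFSR at 24 weeks | event at week 8 | event at week 8 |
| DOR | week 8 − week 16 = −8 weeks | not computed |

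Section 3.11.1.1 does not close the gap. It covers analyses that use the progression date. DOR and PFSR use that date; the BOR window in 8.3.2.2 does not.

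**4. Who is not affected.** Subjects with a confirmed response before initial PD are classified the same way under both texts. Table 4.1-1 in Appendix 3, which "provides a summary of the overall response status calculation at each time point", returns PD whenever a new lesion or non-target PD is recorded. Subjects in whom either persists therefore cannot become late responders.

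**5. Size per subject.** With n = 40 (Parts D and E): 1/40 = 2.5 points. With n = 25 (Part C cohorts, section 8.1.2): 1/25 = 4.0 points.

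**6. Illustration.** The documents give no rate of first response after PD. I assume 10 of 40 respond before PD and 0 to 3 more respond only afterwards. The limits of the exact two-sided 95% CI are the Beta quantiles (0.025; x, n − x + 1) and (0.975; x + 1, n − x).

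| Responders | ORR | Exact 95% CI | Width (points) |
|---|---|---|---|
| 10/40 | 25.0% | 12.7–41.2% | 28.5 |
| 11/40 | 27.5% | 14.6–43.9% | 29.3 |
| 12/40 | 30.0% | 16.6–46.5% | 30.0 |
| 13/40 | 32.5% | 18.6–49.1% | 30.6 |

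The shift is 0 to 7.5 points, against intervals about 28 to 31 points wide.

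**The case against.** The strongest reply is that the stop at progression is already in the plan. Section 8.3.2.2 says BOR follows RECIST 1.1, section 5.4 names Appendix 3 as the study's RECIST text, and Appendix 3 ends BOR at progression. On that reading 8.3.2.2 gives only the outer data window. The confirmation requirement is likewise absent from 8.3.2.2 and has to come from Appendix 3. The subject is then a non-responder and has no DOR. This reading is possible and may be what was meant. But 8.3.2.2 states its own, different window, does not cite the Appendix 3 stop, and nothing says which text prevails.

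A second reply is that the negative DOR depends on bringing 3.11.1.1 into 8.3.2.2. That is true, but 3.11.1.1 applies by its own terms to any analysis using the progression date, and DOR is one.

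A third reply is rarity, and this stands. If target-lesion PD falls at the first scan, the sum must go from at least 120% to at most 70% of baseline, a fall of at least 1 − 70/120 = 42%. In the example above it happens within 8 weeks, and it must then be confirmed. Treatment past PD also needs investigator-assessed benefit and discussion with the Medical Monitor. The count of 0 to 3 is an assumption, and no threshold is crossed.

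The assessor wording is an editorial matter. Section 5.4 points clearly to the investigator, and the main point does not depend on it.

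**Conclusion.** The concern holds. The two BOR definitions differ, the protocol permits the situation in which they diverge, and no text settles it. Following 8.3.2.2 as written can make one subject a responder, a PFSR failure and a negative DOR value at once.

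The effect is 2.5 points of ORR per affected subject with n = 40 and 4 points with n = 25. The number of such subjects is unknown, probably small and possibly zero. The 7.5-point upper end in the illustration rests on the assumed three late responders. No formal decision depends on it. The text should be corrected before the efficacy analysis, because the rule as stated produces an incoherent result and the correction is already in the plan's own appendix.

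**What to change.** In section 8.3.2.2:

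- End the BOR window at the earlier of initial RECIST v1.1 progression, dated as in 3.11.1.1, and the start of subsequent anti-cancer therapy. State that CR and PR need the confirmation required by Appendix 3, sections 4.1.1 and 4.2.
- Use this BOR for both ORR and DOR.
- List responses first seen after initial progression separately, so they stay visible without entering ORR.
- Name one assessor for ORR and DOR, the investigator, in line with section 5.4. Report any central review separately.

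The cost is about two sentences of text and one extra listing. No treatment, visit or scan changes. ORR may come out slightly lower than under the present 8.3.2.2 wording.

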8.3.2.3 Immunogenicity

The third secondary objective of immunogenicity will be assessed by the following endpoint:

- Frequency of positive ADA to BMS-986156 or nivolumab.

8.4 Analyses

8.4.1 Demographics and Baseline Characteristics

Frequency distributions of gender and race will be tabulated. Summary statistics for age, body weight, and height will be tabulated.

8.4.2 Safety Analyses

All recorded AEs will be listed and tabulated by system organ class, preferred term and treatment. Vital signs and clinical laboratory test results will be listed and summarized by treatment. Any significant PE findings and clinical laboratory results will be listed. ECG readings will be evaluated by the Investigator and abnormalities, if present, will be listed.

8.4.3 Efficacy Analyses

Listing of tumor measurements will be provided by subject and study day in each arm and dose level. Individual subject's BOR will be listed based on RECIST 1.1.

To describe the antitumor activity of BMS-986156 alone or in combination with nivolumab, ORR will be calculated. ORR and corresponding 2-sided exact 95% exact CI by the Clopper and Pearson method will be provided by treatment and dose level. Median duration of response and corresponding two-sided 95% CI will be reported by treatment and dose level. Duration of response will be analyzed using the Kaplan-Meier method.

In addition, PFSR, the probability of a subject remaining progression free or surviving to 24 weeks, will be estimated by the Kaplan-Meier methodology, by treatment and dose level. The corresponding 90% CI will be derived based on Greenwood formula. PFSR at month 12 will be estimated using the same method for the combination treatment BMS-986156 and nivolumab.

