As a Phase 1 dose-escalation trial, the sample size at each dose in these arms depends on observed toxicity and posterior inference. Approximately 60 subjects are expected to be treated during the dose-escalation phase (around 30 subjects for BMS-986156 monotherapy and around 30 subjects for BMS-986156 in combination with nivolumab). Initially up to 3 subjects will be treated at the starting dose levels of BMS-986156 or BMS-986156 in combination with nivolumab. Additional cohorts of approximately 3 evaluable subjects will be treated in recommended dose levels per BLRM (-Copula) during the dose-escalation phase. At most 12 DLT-evaluable subjects will be treated at each dose level.

Cohort Expansion:

Part E includes two cohorts with one as Cervical and another one as the mixed tumors for signal seeking and exploration of Q4W dosing. Due to the purpose of signal confirming in cervical cancer and heterogeneity of response rates of the mixed tumors cohort, approximately 40 subjects are planned for each cohort in part E. For initial safety evaluation of 480 mg BMS-986156/480 mg nivolumab Q4W in Part E, 6 subjects will be enrolled and followed for a minimum of 2 weeks (please refer to [Section 3.7](#) for the rationale for 2 week period) prior to opening Part E to full enrollment.

The planned sample size for each of the expansion cohorts serve as a guidance. Final decision will be made by the sponsor based on totality of data available by then.

If in a cohort of 40 subjects 10, or 15 responses are observed, then the lower limit of the one-sided 90% exact binomial CI for the ORR is 16%, and 27% respectively. These calculations are made using the Clopper-Pearson method for exact confidence intervals. If the true ORR in a tumor type is 40%, then with 40 subjects in a tumor type, there is 93% chance of observing at least 12 responses, and 87% chance of observing at least 13 responses, and there is 7% chance of observing 11 or fewer responses (false negative rate).

Primary Endpoints:

- The primary objective of the study is to establish MTD/MAD/alternate dose(s). The assessment of safety will be based on the incidence of AEs, serious adverse events (SAEs), adverse events leading to discontinuation, and deaths. In addition clinical laboratory test abnormalities will be examined.

Secondary endpoints:

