- The ORR, duration of response, and progression free survival rate (PFSR) at 24 weeks will be assessed based on RECIST v1.1 criteria. The above will be determined based on tumor measurements occurring every 8 weeks during the Treatment Period.
- Pharmacokinetics: Selected BMS-986156 parameters, such as Cmax, Ctough, Tmax, T-HALF, AUC-(TAU), CLT and AI, will be assessed, if feasible, from concentration-time data during Cycle 1 and Cycle 3.
- Immunogenicity: Incidence of specific ADA to BMS-986156 and or nivolumab. Samples will be collected at multiple time points.

[figure not shown]
Analyses:

Safety analysis: All recorded adverse events will be coded according to the most current version of MedDRA, listed and tabulated by system organ class, preferred term, treatment arm, and dose level. Vital signs and clinical laboratory test results will be listed and summarized by treatment arm and dose. Any significant physical examination findings and results of clinical laboratory test will be listed. ECG listings will be evaluated by the investigator and abnormalities, if present, will be listed.

Efficacy analysis: Listing of tumor measurements will be provided by subject and study day in each arm and dose level. Individual subject's BOR will be listed based on RECIST v1.1.

To describe the anti-tumor activity of BMS-986156 in single agent and in combination with nivolumab, ORR will be calculated. ORR and corresponding 2-sided exact 95% exact confidence interval by the Clopper and Pearson method will be provided by treatment arm and dose level. Median duration of response and corresponding two-sided 95% confidence interval will be reported by treatment arm and dose level. Duration of response will be analyzed using the Kaplan-Meier method. PFSR at 24 weeks will be estimated by the Kaplan-Meier methodology and the corresponding 90% confidence interval will be presented.

Pharmacokinetic analysis: PK parameters for BMS-986156 will be calculated using non-compartmental analyses. All individual PK parameters will be listed including any exclusions and reasons for exclusion from summaries. Summary statistics will be tabulated for each PK parameters by treatment and study day/week. BMS-986156 PK dose dependency will be assessed in Part A and B. PK scatter plots of Cmax and AUC(TAU) versus dose may be provided for each day measured. Dose proportionality of BMS-986156 when administered alone or co-administered with nivolumab may also be assessed based on a power model.

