8.1.2 Cohort Expansion

Part C contains 2 cohorts of 25 subjects each in monotherapy cohort expansion,. Each cohort in the combination cohort expansion phase (parts D and E) will contain approximately 40 subjects. Forty subjects in parts D and E are planned with the goal of achieving a width of approximately 20% in the 95% confidence interval for ORR, and to provide additional information on safety. Patients in any cohort who discontinue for reasons other than disease progression, death, or treatment-related toxicity may be replaced.

For initial safety evaluation of 480 mg BMS-986156/480 mg nivolumab Q4W in Part E, 6 subjects will be enrolled and followed for a minimum of 2 weeks (please refer to [Section 3.6](#) for the rationale for 2 week period) prior to opening Part E to full enrollment.

If in a cohort of 40 subjects, 10 or 15 responses are observed, then the lower limit of the one-sided 90% CI for the ORR would be 16%, and 27% respectively. These calculations are made using the Clopper-Pearson method for exact confidence intervals. If the true ORR in a tumor type is 40%, then with 40 subjects there is 93% chance of observing at least 12 responses, and 87% chance of observing at least 13 responses, and there is 7% chance of observing 11 or fewer responses.

Continuous interim evaluations and monitoring of safety and efficacy based on the totality of data will be carried out throughout the expansion phase. Decisions regarding continuing enrollment based on these evaluations will be made through discussion between the Sponsor and investigators based on totality of data and overall clinical activity (such as but not limited to duration of response, quality of response, clinical assessment of response and/or SD and safety). The number of subjects receiving treatment of the planned sample size is approximate and may exceed the specified numbers due to unknown time to response and true recruitment rate (i.e additional participants may be enrolled to compensate the 25%-35% of the screening failure rate in combination with the non response evaluable rate to account for participants who may drop out of the study without being evaluable for response and/or true recruitment rate is much higher than anticipated and thus, Sponsor will examine on the totality of data to determine the benefit/risk ratio as well as overall clinical activity when making the final Go/no Go decision.

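### Section 8.4.3 groups ORR, duration of response and 24-week PFSR by treatment and dose level only, which does not by itself yield the per-cohort estimates that Section 8.1.2 sizes the expansion for

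*Combined protocol and SAP*

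**What the plan says.** **Analysis text.** Section 8.4.3 gives the rule for ORR: "ORR and corresponding 2-sided exact 95% exact CI by the Clopper and Pearson method will be provided by treatment and dose level". Median DOR has the same grouping. The 24-week PFSR "will be estimated by the Kaplan-Meier methodology, by treatment and dose level". For the later time point, "PFSR at month 12 will be estimated using the same method for the combination treatment BMS-986156 and nivolumab", with no other grouping named.

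**Synopsis, Efficacy analysis.** For ORR, the "confidence interval by the Clopper and Pearson method will be provided by treatment arm and dose level"; DOR is grouped likewise. For PFSR there is no grouping: "PFSR at 24 weeks will be estimated by the Kaplan-Meier methodology and the corresponding 90% confidence interval will be presented".

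**Endpoint definition.** Section 8.3.2.2: "ORR is defined as the proportion of all treated subjects whose BOR is either a CR or PR". Section 8.2 bases efficacy on all treated subjects. Neither brings in cohort.

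**Sizing text.** Section 8.1.2 plans about 40 subjects in each Part D and Part E cohort and 25 in each of the two Part C cohorts. It links the 40 to the width of the 95% interval for ORR, and gives its probabilities per tumor type: "If the true ORR in a tumor type is 40%, then with 40 subjects there is 93% chance of observing at least 12 responses". The synopsis matches: "If the true ORR in a tumor type is 40%, then with 40 subjects in a tumor type".

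**Doses.** The synopsis assigns all of Part D to 240 mg BMS-986156 plus 240 mg nivolumab Q2W, and both Part E cohorts to 480 mg plus 480 mg Q4W. Section 1.6 shows that 240/240 mg was also a Part B dose level.

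**The concern.** Treatment and dose level separate the escalation groups in Parts A and B, but not the expansion cohorts. Within Part D every subject has the same treatment and dose, so the stated grouping cannot tell NSCLC from cervical, bladder, head and neck, ovarian or hepatocellular cancer. Within Part E it cannot tell cervical cohort 9 from mixed cohort 10. Part B subjects at 240/240 mg have the same treatment and dose as Part D.

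The expansion is justified cohort by cohort. Section 3.5 gives confirmation of a signal as the reason for the cervical cohort in Part E and, separately, varied response rates as the reason for the size of cohort 10. A table built strictly to Section 8.4.3 would not show a cervical response rate.

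Month-12 PFSR is stated only for the combination treatment, so it could span Parts B, D and E. Section 3.2 offers treatment beyond 48 weeks only in Parts D and E.

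At stake is whether the planned efficacy tables report the quantities that the expansion was sized to estimate.

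**Working it through.** **1. The plan's own figures, and the unit they belong to.** Inputs from Section 8.1.2: n = 40, true ORR 40%, and 10 or 15 responders.

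Binomial tail, P(X ≥ r) = Σ C(40,k) 0.4^k 0.6^(40−k) for k = r to 40:
- P(X ≥ 12) = 0.929 (stated 93%)
- P(X ≥ 13) = 0.871 (stated 87%)
- P(X ≤ 11) = 0.071 (stated 7%)

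Clopper-Pearson lower limit, the α quantile of Beta(x, n − x + 1), with α = 0.10 one-sided:
- 10/40: 16.2% (stated 16%)
- 15/40: 27.1% (stated 27%)

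All five reproduce at n = 40, that is, for one cohort or tumor type.

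**2. Size of the groups that Section 8.4.3 defines, read literally.**
- Part D: 6 × 40 = 240
- Part E: 2 × 40 = 80
- Part D plus Part B at 240/240 mg: the Part B number cannot be fixed from the documents. Section 8.1.1 caps a dose level at 12 DLT-evaluable subjects. The safety update in Section 1.6 refers to 27 subjects at this combination, but Section 3.1 lets Part D begin while Part B continues, so the 27 may not all be additional. Part B is therefore left out of the main illustration.

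**3. What one estimate across cohorts could look like (assumed counts).** Two-sided 95% Clopper-Pearson limits are the 0.025 quantile of Beta(x, n − x + 1) and the 0.975 quantile of Beta(x + 1, n − x).

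| Group | Responders | ORR | 95% CI |
|---|---|---|---|
| One active Part D cohort | 16/40 | 40% | 24.9 to 56.7% |
| Each of five other Part D cohorts | 4/40 | 10% | 2.8 to 23.7% |
| Part D combined | 16 + 5 × 4 = 36/240 | 15.0% | 10.7 to 20.2% |
| Part E, cohorts at 16/40 and 4/40 combined | 20/80 | 25% | 16.0 to 35.9% |

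The combined Part D interval lies wholly below the active cohort's interval (20.2% < 24.9%). Adding 12 Part B subjects with one responder changes little: 37/252 = 14.7% (10.6 to 19.7%).

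**4. Range over the assumption.** Let the active cohort have 12 to 20 responders (30% to 50%) and each of the others 2 to 6. The combined ORR runs from (12 + 5 × 2)/240 = 9.2% to (20 + 5 × 6)/240 = 20.8%.

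**5. Precision given up by reporting per cohort.** At an observed 25%:
- 10/40: 12.7 to 41.2%, width 28.5 points
- 60/240: 19.7 to 31.0%, width 11.3 points

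**The case against.** The strongest reply is that the plan, read as a whole, already means per cohort. Section 8.1.2 ties a 95% interval for ORR to a cohort of about 40, and Section 8.4.3 reports a 95% interval for ORR. This stands as evidence of intent for ORR. It does not reach DOR or PFSR, and it does not change the rule that Section 8.4.3 states.

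A second reply is that the synopsis's treatment arm could include cohort. Usage is mixed: Section 3.1 calls the Part C expansion an arm, while the synopsis entry on study duration uses the word for monotherapy versus combination. In Section 8.4.3 only the tumor-measurement listing uses it; the ORR, DOR and PFSR sentences do not.

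A third reply is that little harm follows. This largely stands. Best overall response is listed per subject, cohort is assigned through the IVRS, no hypothesis is formally tested, and go/no-go rests on the totality of data.

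A reader might infer more: that the sponsor has decided to pool tumor types, that per-cohort results will not be produced, or that an active cohort will be missed. The documents do not support any of these. No sentence says that cohorts or Parts B and D will be combined, nothing forbids a further breakdown, and no decision rule uses a pooled rate. Nor are the Section 8.1.2 figures wrong; they are correct for the unit they name.

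**Conclusion.** The point holds as a mismatch between the stated grouping and the sizing unit, and should be fixed. Section 8.4.3 does state a grouping, and for Parts D and E that grouping does not separate the cohorts. No visible analysis text supplies a cohort breakdown.

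The possible distortion is large for an individual cohort: 40% against 15.0% in the illustration, or 30 to 50% against 9.2 to 20.8% over the assumed range. Those counts are assumptions chosen to show the mechanism, not predictions, and they use the nominal cohort size of 40. For Part C the unit is 25 as given in Section 8.1.2. Whether Part B subjects at 240/240 mg would be combined with Part D is a possibility left open by the wording, not something the plan states.

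The consequence is limited because efficacy is secondary and descriptive and Section 8.1.2 already implies the cohort as the unit for ORR.

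**What to change.** In Section 8.4.3 and the synopsis:
- Report ORR with its exact 95% CI, DOR and 24-week PFSR by treatment and dose level for Parts A and B, and by expansion cohort for Parts C, D and E. In the synopsis this also supplies the grouping that the PFSR sentence lacks.
- Report month-12 PFSR by expansion cohort for Parts D and E.
- For cohort 10, which would still mix five tumor types, also show response counts by tumor type, descriptively.
- Label any figure pooled across cohorts as supplementary.

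This keeps Part B apart from Part D, and keeps cervical cohorts 4 and 9, which have different schedules, apart from each other.

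**Cost.** Wording in two places and a few more tables. Cohort assignment is already recorded, and sample size and conduct do not change. Intervals are wider than pooled ones, as shown in step 5 of the working. Median DOR may not be estimable in cohorts with few responders; individual durations would be listed there instead.
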